6.2.3. Duration of Complete Response

Duration of complete response (DoCR) is defined, for participants with a CR per Lugano Response Classification Criteria 2014, as the time from the first documentation of a CR until PD, or death due to any cause, whichever occurs first.

DoCR (months) = [date of event or censoring – first date of CR +1]/30.4375

DoCR will be analyzed in the same way as that is for DoR as described in Section 6.2.2.

6.2.4. Progression-free Survival

Progression-free survival (PFS) is defined as the time from the 'start date' until PD per Lugano Response Classification Criteria 2014, or death due to any cause, whichever occurs first.

PFS data will be censored on the date of the last adequate tumor assessment for patients who do not have an event (PD or death), for patients who start a new anti-cancer therapy prior to an event or for patients with an event after two or more missing tumor assessments. Patients who do not have an adequate baseline tumor assessment or who do not have an adequate post-baseline tumor assessment will be censored on the 'start date' unless death occurred on or before the time of the second planned tumor assessment (i.e. \leq 22 weeks after 'start date') in which case the death will be considered an event.

The censoring and event date options to be considered for the PFS analysis are presented in Table 6.

PFS (months) = [date of event or censoring – 'start date' +1]/30.4375

Table 6 Outcome and event dates for PFS analyses

Scenario	Date of event/censoring	Outcome
No adequate baseline assessment	'Start date' ^a	Censored ^a
PD or death 
 - After at most one missing or inadequate post-baseline tumor assessment, OR - ≤ 22 weeks after 'start date' 	Date of PD or death	Event
PD or death 
 - After 2 or more missing or inadequate post-baseline tumor assessments 	Date of last adequate tumor assessment ^b documenting no PD before new anti-cancer therapy is given or missed tumor assessments	Censored
No PD and no death	Date of last adequate tumor assessment ^b documenting no PD before new anti-cancer therapy is given or missed tumor assessments	Censored
Treatment discontinuation due to 'Disease progression' without documented progression	Not applicable	Information is ignored. Outcome is derived based on documented progression only.
New anti-cancer therapy given	Date of last adequate tumor assessment ^b documenting no PD before new anti-cancer therapy is given or missed tumor assessments	Censored

^a However if the patient dies ≤ 22 weeks after 'start date' the death is an event with date on death date

^b If there are no adequate post-baseline assessments prior to PD or death, then the time without adequate assessment should be measured from the 'start date'; if the criteria were met the censoring will be on the 'start date'.

Kaplan-Meier estimates (product-limit estimates) will be presented and displayed graphically as appropriate, by treatment group, together with a summary of associated statistics including the median PFS time with two-sided 95% CIs. In particular, the PFS rate at 3, 6, 9, 12, 18 and 24 months (and in subsequent 12-month increments as appropriate) will be estimated with corresponding 2-sided 95% CIs. The CIs for the median will be calculated according to Brookmeyer and Crowley (1982) and the CIs for the survival function estimates at the time points defined above will be derived using the log-log transformation according to Kalbfleisch and Prentice (2002) (conftype=loglog default option in SAS Proc LIFETEST) with back transformation to a CI on the untransformed scale. The estimate of the standard error will be computed using Greenwood's formula.

Frequency (number and percentage) of patients with each event type (PD or death) and censoring reasons will be presented by treatment group.

Reasons for censoring will be summarized according to the categories in [Table 7](#) following the hierarchy shown.

Table 7 PFS Censoring Reasons and Hierarchy

Hierarchy	Condition	Censoring Reason
1	No adequate baseline assessment	No adequate baseline assessment
2	Start of new anti-cancer therapy	Start of new anti-cancer therapy
3	Event after 2 or more missing or inadequate post-baseline tumor assessments/ 'start date'	Event after 2 or more missing assessments ^a
4	No event and [withdrawal of consent date \geq 'start date' OR Follow Up Discontinuation Reason = 'withdrawal by subject']	Withdrawal of consent
5	No event and lost to follow-up in any disposition page	Lost to follow-up
6	No event and [EOS present OR disposition page for any epoch after screening says patient will not continue into any subsequent phase of the study] and no adequate post-baseline tumor assessment	No adequate post-baseline tumor assessment
7	No event and none of the conditions in the prior hierarchy are met	Ongoing without an event

^a 2 or more missing or inadequate post-baseline tumor assessments.

The PFS time or censoring time and the reasons for censoring will also be presented in a patient listing.

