### **Progression Free Survival**

PFS is defined as the time from the date of first dose until PD per Lugano Response Classification Criteria 2014, or death due to any cause, whichever occurs first.

PFS will be censored as follows:

- For participants who do not have an event (PD per Lugano Response Classification Criteria 2014 or death due to any cause), censoring will occur on the date of the last adequate disease assessment;
- For participants who start a new anticancer therapy prior to an event, censoring will occur on the date of the last adequate disease assessment before the new anticancer therapy;
- For participants with an event after a gap of 2 or more missing disease assessments, censoring will occur on the date of the last adequate disease assessment before the gap;
- Participants who do not have an adequate post-baseline disease assessment will be censored on the date of first dose of study intervention unless death occurs on or before the time of the second planned disease assessment (ie,  $\leq 24$  weeks after the date of first dose) in which case the death will be considered an event.

PFS will be summarized using Kaplan Meier method and displayed graphically. Median PFS and 2-sided 95% CI will be provided.

PFS will be summarized by dose levels for Phase 1b and Phase 2 of the study separately.

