6.2.2. Duration of Response

Duration of response (DoR) is defined, for participants with an OR per Lugano Response Classification Criteria 2014, as the time from the first documentation of objective response (CR or PR) to the date of first documentation of PD or death due to any cause.

If a patient has not had an event (PD or death), DoR is censored at the date of last adequate tumor assessment. The censoring rules for DoR are as described in [Table 4](#).

DoR (months) = [date of event or censoring – first date of OR +1]/30.4375

Table 4 Outcome and Event Dates for DoR Analyses

Scenario	Date of event/censoring	Outcome
PD or death - After at most one missing or inadequate post-baseline tumor assessment, OR - ≤ 22 weeks after 'start date'	Date of PD or death	Event
PD or death - After 2 or more missing or inadequate post-baseline tumor assessments	Date of last adequate tumor assessment ^a documenting no PD before new anti-cancer therapy is given or missed tumor assessments	Censored
No PD and no death	Date of last adequate tumor assessment ^a documenting no PD before new anti-cancer therapy is given or missed tumor assessments	Censored
Treatment discontinuation due to 'Disease progression' without documented progression	Not applicable	Information is ignored. Outcome is derived based on documented progression only.
New anti-cancer therapy given	Date of last adequate tumor assessment ^a documenting no PD before new anti-cancer therapy is given or missed tumor assessments	Censored

^a If there are no adequate post-baseline assessments prior to PD or death, then the time without adequate assessment should be measured from the 'start date'; if the criteria were met the censoring will be on the 'start date'.

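### SAP Table 6 omits the protocol's gap condition for PFS, so isolated missed scans can censor a progression; the no-event row of Tables 4 and 6 also contradicts the SAP's own text

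*SAP*

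**What the plan says.** **Event rule for PFS.** Protocol 9.4.3.1 sets out one case: "For participants with an event after a gap of 2 or more missing disease assessments". Censoring is then at the last adequate assessment before that gap. The SAP 6.2.4 text has "for patients with an event after two or more missing tumor assessments", and the matching row of Table 6 has "After 2 or more missing or inadequate post-baseline tumor assessments". Neither uses the word gap, or says that the missed scans must be consecutive or immediately before the event. The companion row of Table 6 counts a progression or death as an event after at most one missing or inadequate assessment, or at any time up to 22 weeks from the start date.

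**Event rule for DoR and DoCR.** SAP Table 4 has "PD or death - After 2 or more missing or inadequate post-baseline tumor assessments", and SAP 6.2.3 applies the DoR method to DoCR. The protocol's DoR and DoCR paragraphs are also worded as a count, without a gap.

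**Participants without an event.** The SAP 6.2.4 text reads "PFS data will be censored on the date of the last adequate tumor assessment for patients who do not have an event (PD or death", and SAP 6.2.2 says the same for DoR. The protocol agrees: "censoring will occur on the date of the last adequate disease assessment". In Tables 4 and 6, however, the date cell for this group is the last adequate assessment "documenting no PD before new anti-cancer therapy is given or missed tumor assessments".

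SAP 2.1 declares no change from the protocol's analysis.

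**The concern.** A censoring rule should give one status and one date for every participant record. These rules can give more than one.

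In the event row, a participant with two scattered missed scans and a clean scan at the visit just before progression has a well-dated progression. The protocol counts it. Table 6 taken at its word censors it, and the censoring date is also open. Chances to miss a scan build up with time on study, so the participants most exposed are those who progress late.

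In the no-event row, adequate scans after a missed visit would be ignored. That shortens observed event-free follow-up and contradicts the paragraph that the table is meant to implement.

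Results are shown by dose level in a Phase 1b of about 20 participants, so one misclassified record can visibly move a Kaplan-Meier curve.

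**Working it through.** The plan gives no figure to reproduce here. The check sets out the scan calendar, works two illustrative records, and computes how often the readings differ.

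**Scan calendar.** The schedule of activities places scans at C3D1, C6D1, C9D1, C12D1, C18D1 and C24D1, in 28-day cycles. Day = (cycle − 1) × 28, which gives weeks 8, 20, 32, 44, 68 and 92.

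**Participant A** (adequate at weeks 8, 32 and 68; missed at 20 and 44; progression at 92). PFS months = (days + 1)/30.4375, as in SAP 6.2.4.

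| Reading | Status | PFS |
|---|---|---|
| Protocol: no two-scan gap | Event, week 92 | 645/30.4375 = 21.2 |
| Count; last adequate scan (SAP text) | Censored, week 68 | 477/30.4375 = 15.7 |
| Count; before the second miss (Table 6 cell) | Censored, week 32 | 225/30.4375 = 7.4 |
| Count; before the first miss (Table 6 cell) | Censored, week 8 | 57/30.4375 = 1.9 |

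**Participant B** (response at week 8; weeks 20 and 32 missed; adequate scans without progression at 44 and 68; no event). By the SAP text and the protocol, DoR is censored at week 68: (476 − 56 + 1)/30.4375 = 13.8 months. By the table cell it is censored at week 8: 1/30.4375 = 0.03 months. PFS is 15.7 against 1.9 months.

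**How often the event readings differ.** Let q be the chance that a scan is missed or inadequate, independent between scans. The documents give no value, so 5% to 20% is assumed. For a progression found at a scan with k earlier scans:
- count reading: P(censored) = 1 − (1 − q)^k − kq(1 − q)^(k−1)
- gap reading, with the two scans just before both missed: P(censored) = q²

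At q = 10% and week 92 (k = 5): 1 − 0.5905 − 0.3281 = 8.1%, against 0.1² = 1.0%.

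| Progression found at | Count, q = 10% | Gap, q = 10% |
|---|---|---|
| C9D1 (k = 2) | 1.0% | 1.0% |
| C12D1 (k = 3) | 2.8% | 1.0% |
| C18D1 (k = 4) | 5.2% | 1.0% |
| C24D1 (k = 5) | 8.1% | 1.0% |

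At C24D1 the figures are 2.3% against 0.25% for q = 5%, and 26.3% against 4.0% for q = 20%. The 22-week exception does not alter the table. A progression found at either of the first two scans has at most one earlier scan to miss.

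**Over all progressions.** This adds the assumption of exponential PFS with median 12.1 months, the protocol's L-MIND figure, with detection at the first scan not missed up to week 92. At q = 10%, 4.8% of detected progressions are censored under the count and 1.9% under the gap. If all 20 participants progressed, the excess is 20 × 0.029 = about 0.6 of a participant. At q = 5% it is 1.3% against 0.5%, about 0.2.

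**No-event row.** Among event-free participants with an adequate scan at C12D1, the share with at least one of the three earlier scans missed is 1 − (1 − q)³. This is 14% at q = 5%, 27% at 10% and 49% at 20%. Read literally, the row would shorten follow-up for these participants.

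**The case against.** A reader might infer that the SAP totals every missed scan from baseline. It does not say so. The footnote to Tables 4 and 6 points the other way: "If there are no adequate post-baseline assessments prior to PD or death, then the time without adequate assessment should be measured from the 'start date". That describes an interval without assessment, which suits a gap and which a running total would not need. With SAP 2.1 declaring no change, the likely intention is the protocol's rule. This stands, and it is why the defect is one of wording that admits two answers. It does not remove the defect. The footnote covers only participants with no adequate post-baseline scan, and the rows that a programmer will code give a bare count.

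A reader might also infer that the SAP departs from the protocol's event rule for DoR and DoCR. It does not, because the protocol's wording there is equally a count. Only the no-event row conflicts for those endpoints.

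Nor does the no-event row turn documented progression into censoring: the people it covers have none. It only shortens their censored times.

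It can be argued that the SAP text governs the no-event row, and that Tables 5 and 7 list a missed-scan censoring reason only for participants with an event. Both are fair, and they support the proposed correction. But the phrase remains in the table. A participant still on study and cut short by it would be summarised as ongoing without an event, so the summary of reasons would not show the loss. The per-patient PFS listing would help someone looking for it.

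Finally, censoring a progression after a true gap is what the protocol intends, and is not criticised here.

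**Conclusion.** Wrong as written, with low impact. For PFS, the SAP text and Table 6 leave out the protocol's gap condition and so allow a record such as participant A's to be censored where the protocol counts an event. For PFS, DoR and DoCR, the no-event row contradicts both the SAP's own paragraphs and Protocol 9.4.3.1.

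The discrepancy in events starts only at C12D1. At a 10% miss rate it reaches about 7 percentage points for a progression found at week 92, and about 3 points over all progressions. These sizes rest on assumed, independent miss rates and, for the overall figure, on an assumed exponential PFS. The two worked records do not depend on those assumptions.

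The endpoints are secondary and descriptive, no hypothesis is tested, about 20 participants are involved, and Phase 2 will not be initiated.

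**What to change.** - **Event rows (SAP 6.2.4 text, Tables 4 and 6, and the matching conditions in Tables 5 and 7):** state that a progression or death immediately after two or more consecutive missing or inadequate scheduled assessments is censored at the last adequate assessment before that gap. Keep the early-event exception. Its limit is 22 weeks in the SAP and 24 in the protocol, which should be reconciled separately.
- **No-event row (Tables 4 and 6; DoCR by reference):** delete the last four words of the date cell, so that censoring is at the last adequate assessment before any new anti-cancer therapy. The new-therapy row uses the same cell and can be trimmed in the same way.
- **Protocol DoR and DoCR paragraphs:** add the gap wording already used for PFS, so that all three endpoints share one rule.

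The cost is a wording revision and one condition in the derivation program. No new data are needed.

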5.2.10. Adequate Baseline Disease Assessment

Adequate baseline is defined using the following criteria:

- All baseline assessments must be within 42 days prior to and including the 'start date'.
- Baseline lesions must be assessed with an acceptable method of tumor assessment as specified in the protocol and must include PET/CT, or PET and CT, or possibly PET /MRI or PET and MRI in some circumstances.
- At least 1 target, PET-avid lesion must be identified.
- All lesions (target and non-target) must have non-missing assessments. For target lesions, non-missing measurements and the longest diameter should meet the criteria for being measurable; for non-target lesions, non-missing lesions status at baseline.

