6.1.2.1. Main Analysis

- Estimand strategy: All OR data from Phase 2 will be included in the analysis.
- Analysis set: Safety Analysis Set.
- Intercurrent events and missing data: All data collected after an intercurrent event of subsequent anticancer therapy will be excluded. Participants who do not have a post-baseline disease assessment due to early PD, who receive anticancer therapies other than the study treatment prior to achieving an objective response, or who die, experience PD, or stop disease assessments for any reason prior to achieving an objective response will be counted as non-responders. Missing data will be imputed following Section 5.3.
- Analysis methodology: Assessment of response will be made as per investigator using Lugano 2014 response criteria. The analyses will be by treatment group.

Best overall response (BOR) will be assessed based on reported overall responses at different evaluation time points from the 'start date' until documented disease progression, according to the following rules. Only tumor assessments performed before the start of any further anti-cancer therapies will be considered in the assessment of BOR.

CR = at least 1 determination of CR before first documentation of progression

PR = at least 1 determination of PR before first documentation of progression (and not qualifying for a CR)

SD = at least 1 SD assessment \geq 6 weeks after the 'start date' and before first documentation of progression (and not qualifying for CR or PR).

PD = at least 1 PD assessment (and not qualifying for CR, PR or SD).

Not Evaluable (NE): all other cases.

Objective response (OR) is defined as BOR of CR or PR according to Lugano 2014 response criteria.

Patients who do not have an on-treatment tumor assessment due to early progression, who receive anti-tumor therapies other than the study treatments prior to reaching a CR or PR, or who die, progress, or drop out for any reason prior to reaching a CR or PR will be counted as non-responders in the assessment of OR. Each patient will have an objective response status (0: no OR; 1: OR). OR rate (ORR) is the proportion of patients with OR in the analysis set.

ORR by treatment group will be calculated along with the 2-sided 95% CI using the Wilson method (with continuity correction).

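### The SAP censors PFS on Day 1 when the baseline assessment is inadequate, which can drop documented PD and deaths after 22 weeks that the protocol's rules count

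*SAP*

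**What the plan says.** Protocol 9.4.3.1 defines PFS as "time from the date of first dose until PD per Lugano Response Classification Criteria 2014, or death due to any cause". It then gives four censoring rules:

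- no event;
- new anticancer therapy before an event;
- an event following a gap ("For participants with an event after a gap of 2 or more missing disease assessments, censoring will occur" at the last adequate assessment before it);
- no adequate follow-up scan ("Participants who do not have an adequate post-baseline disease assessment will be censored on the date of first dose of study intervention"; the exception is a death within 24 weeks).

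None of the four refers to the baseline scan.

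SAP 6.2.4 widens the last rule: "Patients who do not have an adequate baseline tumor assessment or who do not have an adequate post-baseline tumor assessment will be censored". The censoring date is again the start date. Inadequate baseline is the first row of Table 6 and the first reason in the Table 7 hierarchy, where it is not limited to participants without an event. The one exception is footnote a of Table 6: "However if the patient dies ≤ 22 weeks after 'start date' the death is an event with date on death date".

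SAP 5.2.10 defines an adequate baseline by timing (42 days), imaging modality, at least one PET-avid target lesion, and completeness: "All lesions (target and non-target) must have non-missing assessments". SAP 2.1 gives modifications to the protocol analysis as not applicable.

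**The concern.** Two documents that should give the same PFS derivation do not. A participant whose baseline fails SAP 5.2.10, perhaps through one unrecorded non-target status, is removed at time zero under the SAP even if progression is later documented or death occurs after 22 weeks. A death needs no baseline scan to be recognised. Progression can often still be judged when the baseline images exist and only a field, a date limit or a modality requirement was missed.

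The SAP analyses PFS by dose level. With about 20 Phase 1b participants, at least 2 to 4 per level and about 6 to 9 at the top level, each lost event matters to its curve. Cancelling Phase 2 does not remove the issue, because PFS remains a Phase 1b secondary endpoint in Protocol Section 3.

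**Working it through.** The documents give no PFS event count, power or target, so there is no stated figure to reproduce. The check compares the rules and then illustrates their effect.

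**Step 1: the same participants under both rule sets.** All have an inadequate baseline, no new anticancer therapy and no run of missed scans. Day 1 censoring gives PFS = (0 + 1)/30.4375 = 0.03 months.

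| Course | Protocol 9.4.3.1 | SAP 6.2.4 |
|---|---|---|
| PD at week 20, adequate follow-up scans | event, week 20 | censored Day 1 |
| Death at week 30, adequate follow-up scans | event, week 30 | censored Day 1 |
| Death at week 15 | event, week 15 | event, week 15 |
| PD at week 8, death at week 15 | event, week 8 | event, week 15 (footnote a read literally) |
| No adequate follow-up scan, death at week 23 | event, week 23 | censored Day 1 |
| No adequate follow-up scan, death at week 30 | censored Day 1 | censored Day 1 |

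The first two rows are the conflict. The fourth moves an event date. The fifth would differ even with an adequate baseline, because the early-death limit is 24 weeks in the protocol and 22 in the SAP. The second planned scan, C6D1, falls at (6 − 1) × 28/7 = 20 weeks, or 21 with the 7-day window. That mismatch is a separate matter.

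Table 6 also overlaps with itself. PD at week 20 with an inadequate baseline meets its first row (censored) and its second (event). The text and the Table 7 ranking favour censoring.

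**Step 2: illustration of size.** Assumptions: 20 participants pooled; exponential PFS with a median of 12.1 months (the earlier single-arm study of the doublet, Protocol Section 2); 24 months of follow-up; 15% of events are deaths; 1, 2 or 4 inadequate baselines; 3000 simulated trials. Only the sample size and the median come from the documents.

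| Hazard of affected participants | Number affected | Expected events, protocol → SAP | 12-month PFS, protocol → SAP |
|---|---|---|---|
| Same as others | 1 | 14.94 → 14.22 | 0.498 → 0.498 |
| Same as others | 2 | 14.94 → 13.51 | 0.505 → 0.503 |
| Same as others | 4 | 14.93 → 12.07 | 0.505 → 0.500 |
| Doubled | 1 | 15.11 → 14.24 | 0.489 → 0.500 |
| Doubled | 2 | 15.34 → 13.60 | 0.475 → 0.496 |
| Doubled | 4 | 15.70 → 12.22 | 0.452 → 0.493 |

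With a common hazard, about 0.7 events are lost per affected participant (14.94 − 14.22 = 0.72). The 12-month estimate barely moves, and its standard deviation rises from 0.11 to at most 0.12. With a doubled hazard the estimate rises by 0.011, 0.021 and 0.041.

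**Step 3: dose level.** One participant is 1/9 = 11% to 1/3 = 33% of a curve of 9 or 3. That is a share of participants, not a shift in PFS.

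**The case against.** Several counter-arguments carry weight.

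- *Authority.* Protocol Section 9 lets the SAP modify planned analyses, and only major changes to the primary endpoint need an amendment. The SAP's change log says the baseline criteria were refined on clinical advice. The departure is therefore permitted. What stands against it is that SAP 2.1 does not declare it and no reason is given for applying it to deaths.
- *Progression needs a baseline.* Protocol 8.2 treats new lesions as those appearing after baseline, and Appendix 12 judges some progression by change from baseline. If baseline imaging is truly unusable, follow-up scans may be unevaluable under SAP 5.2.11, and the protocol's own fourth rule would then censor on Day 1. A reader might infer that new lesions can always be called without a baseline; the documents do not support that. For progression, the conflict concerns a usable baseline that fails on a technicality.
- *Response and duration of response.* A reader might infer that the SAP plainly makes the same person a responder with a DoR event and a Day 1 censoring for PFS. The CR rule, "CR = at least 1 determination of CR before first documentation of progression", has no baseline condition, and neither does DoR Table 4. However, SAP 6.1.2.1 goes on to list inadequate baseline as a reason for a best response of not evaluable, which suggests such participants were meant to be non-responders who never enter DoR. Because not evaluable is defined as the residual category, the CR and PR rules as worded still admit them. This is a wording gap, not a proven contradiction.
- *Rarity and disclosure.* PET-avid measurable disease is an entry criterion, the sponsor reviews eligibility, the 42-day limit matches the protocol's imaging allowance, and analyses use cleaned data. Table 7 reasons are tabulated and PFS is listed by participant. This makes the problem small and visible, but it does not put the events back into the estimate.

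**Conclusion.** The discrepancy holds. As written, the SAP applies an undeclared Day 1 censoring rule that the protocol lacks, and it can discard documented PD and deaths after 22 weeks. The protocol would count these only if there is an adequate post-baseline assessment, no earlier new anticancer therapy and no gap of missed assessments. Deaths within 22 weeks are kept by both documents.

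The practical size is limited. The number with an inadequate baseline is not given and is probably small; the 1, 2 and 4 used above are assumptions. PFS is secondary and descriptive, with no hypothesis test. A reader might infer that the rule inflates PFS. The documents do not establish that: the illustration shows essentially no shift under a common hazard, and an upward one only if affected participants are assumed to do worse. What is certain is that any such participant's known event leaves a small dose-level curve.

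**What to change.** Delete the adequate-baseline condition from the SAP 6.2.4 text, the first row of Table 6 (with footnote a) and the first reason in Table 7, so that PFS follows Protocol 9.4.3.1.

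If the sponsor prefers to keep a baseline condition, limit it to progression that cannot be determined without a usable baseline, never apply it to deaths, and declare and justify it in SAP 2.1.

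In either case, align the CR and PR rules in SAP 6.1.2.1 with the inadequate-baseline reason for a not-evaluable response, so that best response, DoR and PFS treat these participants alike.

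The cost is SAP wording and a small change to derivation code, with no new data. SAP Version 2 is tied to Amendment 1 while the protocol is at Amendment 2, so the change can go into the same alignment update.
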